## 8.3.4 Clinical Safety Laboratory Assessments

Refer to Appendix 2 for the list of clinical laboratory tests to be performed and to the SoA for the timing and frequency.

- The investigator or medically qualified designee (consistent with local requirements) must review the laboratory report, document this review, and record any clinically relevant changes occurring during the study in the AE section of the CRF. The laboratory reports must be filed with the source documents. Clinically significant abnormal laboratory findings are those which are not associated with the underlying disease, unless judged by the investigator to be more severe than expected for the participant's condition.
- All protocol-required laboratory assessments, as defined in Appendix 2, must be conducted in accordance with the laboratory manual and the SoA.
- If laboratory values from nonprotocol-specified laboratory assessments performed at the institution's local laboratory require a change in study participant management or are considered clinically significant by the investigator (eg, SAE or AE or dose modification), then the results must be recorded in the appropriate CRF (eg, SLAB).
- For any laboratory tests with values considered clinically significantly abnormal during participation in the study or within 14 days after the last dose of study intervention, every attempt should be made to perform repeat assessments until the values return to normal or baseline or if a new baseline is established as determined by the investigator.

# 8.3.5 **Pregnancy Testing**

- Pregnancy testing:
  - Pregnancy testing requirements for study inclusion are described in Section 5.1.
  - Additional serum or urine pregnancy tests may be performed, as determined necessary by the investigator or required by local regulation, to establish the absence of pregnancy at any time during the subject's participation in the study.

#### 8.3.6 Suicidal Ideation and Behavior Monitoring

#### 8.3.6.1 Clinical Assessments for Suicidal Ideation and Behavior Monitoring

Suicidal ideation and behavior will be prospectively assessed during this study using the C-SSRS. The C-SSRS should be administered by trained raters at the time points indicated in the SoA. In addition, C-SSRS will be administered at any unscheduled visit where safety assessments are performed. The C-SSRS will not be routinely administered at visits with a sole purpose of PK sampling and/or witnessed study intervention administration. Site staff should review the contents of the C-SSRS for completeness.

If the C-SSRS is administered by someone other than the investigator, consider providing the completed C-SSRS to the investigator for review, before their assessment of the participant and to further inform their evaluation.

The C-SSRS is not explicit about whether the participant specifically has ideation at the time of screening. If a participant reports a prior history of ideation/behavior at screening, the assessor should also inquire and document if this is also present at the time of the Screening Visit.

Participants who at any time during this study report suicidal ideation or behavior that is considered to be an AE, either between visits or during visit interviews, must be assessed by the investigator. Participants who report suicidal ideation with intent, with or without a plan or method (i.e., a positive response to items 4 or 5 in the assessment of suicidal ideation on the C-SSRS) or suicidal behavior must be evaluated that day by a psychiatrist or other trained mental health professional who is a licensed psychologist, social worker, or mental health nurse practitioner (or comparable professional qualification in countries outside the United States). After that evaluation, only those participants whose suicidal ideation is considered by the evaluator to be passive, and who expressly deny any intent to act, and who, after evaluation, are not judged to be at serious risk for self-harm during the course of the study may continue in the study; other participants must be discontinued from study participation and receive appropriate clinical follow-up care to ensure their safety. In addition, all AEs of suicidal ideation or behavior must be recorded as an ECI (See Section 8.4.7). Sites are to designate which health care professionals are to be responsible for acute care on-site and to specify referral center(s) to be used for further evaluation.

#### 8.3.7 Rater Expectations and Training for Clinical and Cognitive Assessments

For this study, potential raters of clinical and/or cognitive assessments (BARS [Section 8.3.11], SAS [Section 8.3.11], AIMS [Section 8.3.11], C-SSRS [8.3.6.1], MHIS [Section 8.3.8], MMSE-2 [Section 8.3.9], and NPI [Section 8.3.10]) will be identified based on review of their reported credentials against target minimum credentials for education, prior experience with AD, MCI or similar populations and direct, hands-on experience with study-specific or similar assessments. Persons whose credentials meet or exceed those targets will then be considered 'qualified' as raters in this trial. For the MMSE-2 and NPI, raters will subsequently complete overview, didactic, protocol-specific training before conducting

assessments in this trial. It is recommended that the same rater conducts the same assessments throughout the study for a given participant, where feasible.

All clinical and cognitive assessments will be administered after dosing and following an optional light breakfast provided by the CRU.

## 8.3.8 Rosen-Modified Hachinski Ischemia Scale

The MHIS will be completed by an experienced rater at timepoints specified in Section 1.3 Schedule of Activities.

# 8.3.9 Mini Mental State Examination Second Edition

The paper version of the MMSE-2 (Standard version, both Red and Blue forms) will be administered and scored by a qualified, trained rater at timepoints specified in Section 1.3 Schedule of Activities. Additional information concerning administration, scoring and documentation may also be provided in rater training and in the MOA.

## 8.3.10 Neuropsychiatric Inventory

The paper version of the NPI (12 items) will be administered by a qualified, trained rater at timepoints specified in Section 1.3 Schedule of Activities. Additional information concerning administration, scoring and documentation may also be provided in rater training and in the MOA.

## 8.3.11 Monitoring of Extrapyramidal Symptoms

The Barnes Akathisia Ratting Scale (BARS), Abnormal Involuntary Movement Scale (AIMS) and Simpson Angus Scale (SAS) will be completed by a qualified rater at timepoints specified in Section 1.3 Schedule of Activities.

Refer to the MOA for additional information regarding the BARS, AIMS and SAS.

## 8.3.12 Neurological Exam

The General (Full) Neurological Exam will be performed at the Screening and Baseline visits. The Targeted Neurological Exam will be administered at times specified in the SoA.

The General and Targeted Neurological Exams are contained in Appendix 10.

## 8.4 Adverse Events, Serious Adverse Events, and Other Reportable Safety Events

The definitions of an AE or SAE, as well as the method of recording, evaluating, and assessing causality of AE and SAE and the procedures for completing and transmitting AE, SAE, and other reportable safety event reports can be found in Appendix 3.

Adverse events, SAEs, and other reportable safety events will be reported by the participant (or, when appropriate, by a caregiver, surrogate, or the participant's legally authorized representative).

The investigator and any designees are responsible for detecting, documenting, and reporting events that meet the definition of an AE or SAE as well as other reportable safety events. Investigators remain responsible for following up AEs, SAEs, and other reportable safety events for outcome according to Section 8.4.3.

The investigator, who is a qualified physician, will assess events that meet the definition of an AE or SAE as well as other reportable safety events with respect to seriousness, intensity/toxicity and causality.

## 8.4.1 Time Period and Frequency for Collecting AE, SAE, and Other Reportable Safety Event Information

AEs, SAEs, and other reportable safety events that occur after the participant provides documented informed consent, but before intervention allocation/randomization, must be reported by the investigator for randomized participants only if the event causes the participant to be excluded from the study, or is the result of a protocol-specified intervention, including, but not limited to washout or discontinuation of usual therapy, diet, placebo, or a procedure.

From the time of intervention allocation/randomization through 14 days after cessation of intervention, all AEs, SAEs and other reportable safety events must be reported by the investigator.

Additionally, any SAE brought to the attention of an investigator any time outside the period specified in the previous paragraph also must be reported immediately to the Sponsor if the event is considered related to study intervention.

Investigators are not obligated to actively seek AEs or SAEs or other reportable safety events in former study participants. However, if the investigator learns of any SAE, including a death, at any time after a participant has been discharged from the study, and he/she considers the event to be reasonably related to the study intervention or study participation, the investigator must promptly notify the Sponsor.

All initial and follow-up AEs, SAEs, and other reportable safety events will be recorded and reported to the Sponsor or designee within the time frames as indicated in Table 3.

Exception: A positive pregnancy test at the time of initial screening is not a reportable event unless the participant has received study intervention.

Type of Event	Reporting Time Period: Consent to Randomization/ Allocation (Randomized participants only)	Reporting Time Period: Randomization/ Allocation through Protocol- specified Follow- up Period	Reporting Time Period: After the Protocol- specified Follow- up Period	Time Frame to Report Event and Follow-up Information to Sponsor:
NSAE	Report if: - due to protocol- specified intervention - causes exclusion - participant is receiving placebo run-in or other run-in treatment	Report all	Not required	Per data entry guidelines
SAE	Report if: - due to protocol- specified intervention - causes exclusion - participant is receiving placebo run-in or other run-in treatment	Report all	Report if: - drug/vaccine related. (Follow ongoing to outcome)	Within 24 hours of learning of event
Pregnancy/ Lactation Exposure	Report if: - participant has been exposed to any protocol- specified intervention (eg, procedure, washout or run-in treatment including placebo run-in) Exception: A positive pregnancy test at the time of initial screening is not a reportable event.	Report all	Previously reported – Follow to completion/ termination; report outcome	Within 24 hours of learning of event
ECI (require regulatory reporting)	Report if: - due to intervention - causes exclusion	Report - potential DILI - require regulatory reporting	Not required	Within 24 hours of learning of event
ECI (do not require regulatory reporting)	Report if: - due to intervention - causes exclusion	Report - non-DILI ECIs and those not requiring regulatory reporting	Not required	Within 5 calendar days of learning of event
Cancer	Report if: - due to intervention - causes exclusion	Report all	Not required	Within 5 calendar days of learning of event (unless serious)

Table 3	Reporting Time Periods and Time Frames for Adverse Events and Other
Reportable	Safety Events

Type of Event	Reporting Time Period: Consent to Randomization/ Allocation (Randomized participants only)	Reporting Time Period: Randomization/ Allocation through Protocol- specified Follow- up Period	Reporting Time Period: After the Protocol- specified Follow- up Period	Time Frame to Report Event and Follow-up Information to Sponsor:
Overdose	Report if: - receiving placebo run- in or other run-in medication	Report all	Not required	Within 24 hours of learning of event

DILI=drug-induced liver injury; ECI=event of clinical interest; NSAE=nonserious adverse event; SAE=serious adverse event.

#### 8.4.2 Method of Detecting AEs, SAEs, and Other Reportable Safety Events

Care will be taken not to introduce bias when detecting AEs and/or SAEs and other reportable safety events. Open-ended and nonleading verbal questioning of the participant is the preferred method to inquire about AE occurrence.

#### 8.4.3 Follow-up of AE, SAE, and Other Reportable Safety Event Information

After the initial AE/SAE report, the investigator is required to proactively follow each participant at subsequent visits/contacts. All AEs, SAEs, and other reportable safety events, including pregnancy and exposure during breastfeeding, ECIs, cancer, and overdose will be followed until resolution, stabilization, until the event is otherwise explained, or the participant is lost to follow-up (as defined in Section 7.3). In addition, the investigator will make every attempt to follow all nonserious AEs that occur in randomized participants for outcome. Further information on follow-up procedures is given in Appendix 3.

#### 8.4.4 Regulatory Reporting Requirements for SAE

Prompt notification (within 24 hours) by the investigator to the Sponsor of SAE is essential so that legal obligations and ethical responsibilities towards the safety of participants and the safety of a study intervention under clinical investigation are met.

The Sponsor has a legal responsibility to notify both the local regulatory authority and other regulatory agencies about the safety of a study intervention under clinical investigation. The Sponsor will comply with country-specific regulatory requirements and global laws and regulations relating to safety reporting to regulatory authorities, IRB/IECs, and investigators.

Investigator safety reports must be prepared for SUSARs according to local regulatory requirements and Sponsor policy and forwarded to investigators as necessary.

An investigator who receives an investigator safety report describing an SAE or other specific safety information (eg, summary or listing of SAE) from the Sponsor will file it along with the IB and will notify the IRB/IEC, if appropriate according to local requirements.

#### 8.4.5 **Pregnancy and Exposure During Breastfeeding**

Not applicable

# 8.4.6 Disease-related Events and/or Disease-related Outcomes Not Qualifying as AEs or SAEs

Not applicable

#### 8.4.7 Events of Clinical Interest

Selected serious and nonserious AEs are also known as ECIs and must be reported to the Sponsor.

Events of clinical interest for this study include:

- 1. An overdose of Sponsor's product, as defined in Section 8.5.
- 2. An elevated AST or ALT laboratory value that is greater than or equal to 3X the ULN and an elevated total bilirubin laboratory value that is greater than or equal to 2X the ULN and, at the same time, an alkaline phosphatase laboratory value that is less than 2X the ULN, as determined by way of protocol-specified laboratory testing or unscheduled laboratory testing.\*

\*Note: These criteria are based on available regulatory guidance documents. The purpose of the criteria is to specify a threshold of abnormal hepatic tests that may require an additional evaluation for an underlying etiology. The study-site guidance for assessment and follow up of these criteria can be found in the Investigator Study File Binder (or equivalent).

It may also be appropriate to conduct additional evaluation for an underlying etiology in the setting of abnormalities of liver blood tests including AST, ALT, bilirubin, and alkaline phosphatase that do not meet the criteria noted above. In these cases, the decision to proceed with additional evaluation will be made through consultation between the study investigators and the Sponsor Clinical Director. However, abnormalities of liver blood tests that do not meet the criteria noted above.

- 3. Severe EPS or EPS resulting in study intervention discontinuation
- 4. Suicidal ideation, suicidal behavior
- 5. Treatment-emergent adverse event of new or worsening tardive dyskinesia

#### 8.5 Treatment of Overdose

For purposes of this study, an overdose will be defined as any dose of any drug administered as part of the study exceeding the dose prescribed by the protocol. It is up to the investigator

or the reporting physician to decide whether a dose is to be considered an overdose, in consultation with the Sponsor.

# 8.6 Pharmacokinetics

The decision as to which plasma samples collected will be measured for evaluation of PK will be collaboratively determined by the Sponsor (e.g., samples at lower doses may not be measured if samples at higher doses reveal undetectable drug concentrations). If indicated, these samples may also be measured and/or pooled for assay in an exploratory manner for metabolites and/or additional pharmacodynamic markers.

# 8.6.1 Blood Collection for Plasma MK-8189 and/or Metabolites Assay

Sample collection, storage, and shipment instructions for plasma samples will be provided in the laboratory manual.

## 8.6.2 Blood Collection for Plasma Donepezil Assay

Sample collection, storage, and shipment instructions will be provided in the laboratory manual.

## 8.6.3 Blood Collection for Plasma Memantine Assay

Sample collection, storage, and shipment instructions will be provided in the laboratory manual.

## 8.7 Pharmacodynamics

Pharmacodynamic parameters will not be evaluated in this study.

#### 8.8 Biomarkers

Collection of samples for other biomarker research is also part of this study. The following samples for biomarker research are required and will be collected from all participants as specified in the SoA:

- Blood for Genetic Analysis
- Blood for Exploratory Plasma Biomarkers for AD Diagnosis

## 8.8.1 Planned Genetic Analysis Sample Collection

The planned genetic analysis sample will be drawn for CYP2C9 genotyping and for planned analysis of the association between genetic variants in DNA and drug response. If the IRB/IEC does not approve of the planned analysis of the association between DNA variation and drug response, or if there is a local law or regulation prohibiting the same, data analysis will be limited to CYP2C9 genotyping. Leftover extracted DNA will be stored for FBR if the participant provides documented informed consent for FBR.

Sample collection, storage, and shipment instructions for planned genetic analysis samples will be in the operations/laboratory manual.

# 8.8.2 Exploratory Plasma Biomarkers for Alzheimer's Disease Diagnosis Sample Collection

Sample collection, storage, and shipment instructions for exploratory plasma biomarker samples will be provided in the operations/laboratory manual.

# 8.9 Future Biomedical Research Sample Collection

If the participant provides documented informed consent for FBR, the following specimens will be obtained as part of FBR:

- Leftover DNA for future research
- Leftover main study plasma from MK-8189 and/or metabolites assay stored for future research.

# 8.10 Visit Requirements

Visit requirements are outlined in Section 1.3. Specific procedure-related details are provided in Section 8.

## 8.10.1 Trial Partner/Caregiver Participation

The trial partner/caregiver is required to accompany the participant to the Screening Visit, to sign the trial partner informed consent. This trial partner/caregiver should be willing and make every effort to accompany the participant to all study visits. In the event the trial partner/caregiver in unable to attend a study visit, he/she should discuss alternative arrangements with the site (e.g., participant transportation, return of study intervention and dosing diary) and availability of the trial partner/caregiver to provide and receive input by phone as needed (e.g. questions/instructions related to dosing information captured on dosing diary).

Every effort should be made to maintain the same trial partner/caregiver for the duration of the study. However, if the trial partner/caregiver is unable to continue with the study requirements, the trial partner/caregiver should discuss with the site whether a suitable replacement can be found. If a new trial partner/caregiver is identified, the new trial partner/caregiver will need to sign the trial partner/caregiver informed consent.

# 8.10.2 Screening (Visit 1)

Approximately 6 weeks before intervention randomization, potential participants will be evaluated to determine that they fulfill the entry requirements as set forth in Section 5. Any participants being treated with antipsychotics at Screening must wash off their medications if considered medically appropriate (see Inclusion Criterion No. 10). If a participant has washed-off antipsychotic therapy (minimum 2 week or 5 half-life washout, whichever is

longer) during Screening, the NPI for that participant should be repeated, and will be considered the baseline value.

Participants may be rescreened after consultation with the Sponsor. Rescreening should include all screening procedures listed in the SoA, including consent review. Rescreen procedures cannot be conducted the day prior to intervention randomization if there are Baseline procedures planned per protocol.

Please see the operations manual for eCRF screening data entry requirements prior to randomization.

# 8.10.3 Baseline (Visit 2)

Within 3-5 days prior to study intervention administration, participants will have Baseline safety evaluations per Section 1.3 Schedule of Activities.

# 8.10.4 Intervention Period Visit (Visits 3-9)

# Day 1 (Visit 3)

Participants will return to the CRU on Day 1 for a predose assessments per the SoA. Participants will be administered study treatment by the CRU staff per section 8.1.8. On Day 1, participants will remain at the CRU until the last study assessment is complete and for at least 6 hours following the first administration of study intervention (Day 1).

## **Outpatient CRU Visits (Visits 4-9)**

Participants, not domiciled, will return for CRU visits on Day 4, Day 7, Day 10 (Titration 3 only), Day 14, Day 21 and Day 28. Participants should be fasted upon return to the CRU. Participants will be administered study intervention by CRU staff and safety and PK assessments will be performed per the SoA. Participants will remain at the CRU until the last study assessment is complete. If the dose is the first administration at the next titrated dose level, participants will be required to be supervised by CRU staff for at least 6 hours post dose.

## Participant Daily Home & CRU Requirements

Participants will self-administer study intervention (Section 8.1.8) on days not required to be in the CRU. Participants or trial partners/caregivers will record dosing date, time and number of tablets taken in a study intervention diary.

CRU staff will call the participants daily to check study intervention compliance, review/record AEs and if necessary, remind participants of next scheduled visit.

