# **Intervention Groups and Duration:**

Intervention	Interven-				Route of	Regimen/ Treatment				
Groups	tion Group	Drug	Dose Strongth	Dose Fragueney	Admini-	Period/ Vaccination	Use			
1	Name	Drug	Strength	Frequency	stration	Regimen	Use			
	Active MK-8		4 mg & 12 mg	QD	Oral	Titration 1 4 mg x 2 tabletsDays 1-3;4 mg x 1 tablet &12 mg x 1 tabletDays 4-28 Titration 2 4 mg x 2 tabletsDays 1-3;4 mg x 1 tablet &12 mg x 1 tabletDays 4-6;12 mg x 2 tabletsDays 7-28 Titration 3 4 mg x 1 tabletDays 1-3;4 mg x 1 tabletDays 4-6;12 mg x 2 tabletsDays 4-6;4 mg x 1 tabletDays 4-6;4 mg x 1 tabletDays 4-6;12 mg x 1 tablet &12 mg x 2 tabletsDays 7-9;12 mg x 2 tablets	Experi- mental Treatment			
	Placebo	Placebo	0 mg	QD	Oral	Days 10-28 Titration 1 & 2 2 tablets Days 1-28 Titration 3 1 tablet Days 1-3; 2 tablets Days 4-28	Control			
	QD=Once a	is: day								
Total Number of Intervention Groups/ Arms	2									
Duration of Participation	Each participant will participate in the study for approximately 3 months from the time the participant provides documented informed consent through the final contact. After a screening phase of 42 days, each participant will receive assigned intervention for approximately 28 days. After the end-of-treatment each participant will be followed for 14 days.									

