# 8.10.6 Poststudy (Visit10)

Participants will be required to return to clinic approximately 14 days after the last dose of study intervention for the poststudy visit. If the poststudy visit occurs less than 14 days after the last dose of study intervention, a subsequent follow-up telephone call should be made at 14 days post the last dose of study intervention to determine if any AEs have occurred since the poststudy clinic visit.

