#### 9.6 Statistical Methods

#### Safety:

For primary objective, all AEs and AEs leading to discontinuation of study intervention will be summarized and tabulated.

Summary statistics and plots will be generated for raw laboratory safety tests, 12-lead ECGs, and/or VS as well as for change from baseline, as deemed clinically appropriate. Depending on the safety parameter, the difference from baseline will either be computed on the original scale (raw change from baseline) or on the log scale and back transformed for reporting (percent change from baseline).

For exploratory purposes, summary statistics and plots will be generated for BARS, AIMS, SAS, as well as for change from baseline. Responses to the C-SSRS will be listed. Additionally, summary statistics for change in MMSE-2 and NPI from baseline will be provided.

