## Assessment of causality

- Did the Sponsor's product cause the AE?
- The determination of the likelihood that the Sponsor's product caused the AE will be provided by an investigator who is a qualified physician. The investigator's signed/dated initials on the source document or worksheet that supports the causality noted on the AE form, ensures that a medically qualified assessment of causality was done. This initialed document must be retained for the required regulatory time frame. The criteria below are intended as reference guidelines to assist the investigator in assessing the likelihood of a relationship between the test product and the AE based upon the available information.
- The following components are to be used to assess the relationship between the Sponsor's product and the AE; the greater the correlation with the components and their respective elements (in number and/or intensity), the more likely the Sponsor's product caused the AE:
  - **Exposure:** Is there evidence that the participant was actually exposed to the Sponsor's product such as: reliable history, acceptable compliance assessment (pill

count, diary, etc), expected pharmacologic effect, or measurement of drug/metabolite in bodily specimen?

- **Time Course:** Did the AE follow in a reasonable temporal sequence from administration of the Sponsor's product? Is the time of onset of the AE compatible with a drug-induced effect (applies to studies with investigational medicinal product)?
- Likely Cause: Is the AE not reasonably explained by another etiology such as underlying disease, other drug(s)/vaccine(s), or other host or environmental factors.
- **Dechallenge:** Was the Sponsor's product discontinued or dose/exposure/frequency reduced?
  - If yes, did the AE resolve or improve?
  - If yes, this is a positive dechallenge.
  - If no, this is a negative dechallenge.

(Note: This criterion is not applicable if: (1) the AE resulted in death or permanent disability; (2) the AE resolved/improved despite continuation of the Sponsor's product; (3) the study is a single-dose drug study; or (4) Sponsor's product(s) is/are only used 1 time.)

- Rechallenge: Was the participant re-exposed to the Sponsor's product in this study?
  - If yes, did the AE recur or worsen?
  - If yes, this is a positive rechallenge.
  - If no, this is a negative rechallenge.

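### Scheduled AE questioning falls from daily on drug to one visit in the 14 days off drug, yet the primary AE table pools both periods

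*Combined protocol and SAP*

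**What the plan says.** **On drug.** Under the Intervention Period heading, Section 8.10.4 states: "CRU staff will call the participants daily to check study intervention compliance, review/record AEs and if necessary, remind participants of next scheduled visit". SoA footnote c describes the same daily calls for outpatients. In addition to Day 1, participants "will return for CRU visits on Day 4, Day 7, Day 10 (Titration 3 only), Day 14, Day 21 and Day 28".

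**Off drug.** The synopsis states: "After the end-of-treatment each participant will be followed for 14 days". Section 8.10.6 provides the contact: "Participants will be required to return to clinic approximately 14 days after the last dose of study intervention for the poststudy visit". The SoA window is 14 days after the last dose, plus up to 2. If the visit comes sooner, "a subsequent follow-up telephone call should be made at 14 days post the last dose of study intervention".

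**What counts.** Section 8.4.1 requires that from randomization "through 14 days after cessation of intervention, all AEs, SAEs and other reportable safety events must be reported by the investigator". For the primary objective, Section 9.6 says that "all AEs and AEs leading to discontinuation of study intervention will be summarized and tabulated". Section 9 as given has no on-drug/off-drug split and no denominator of days observed.

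**How AEs are sought.** Section 8.4.2 prefers open-ended questions put to the participant. Inclusion criterion 2 requires an MMSE-2 of 10 to 24. Section 8.4 also allows a caregiver to report.

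**Early stoppers.** Section 7.1 keeps them in the study under the SoA and Section 8.1.9, or under a clarification letter. Section 8.1.9 makes the return visit something they may be asked to attend. It allows poststudy procedures at discontinuation, with a call at the end of follow-up. Section 8.10.5 makes a subset of procedures discretionary. SoA footnote a says that poststudy procedures should be done for them.

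**The concern.** AEs are the primary endpoint, and Section 4.2 says the safety assessment will be used to decide whether longer trials can be supported. If events are asked about every day in one period and once in the next, the two periods do not give comparable rates. A fall in AEs after the last dose could come from the drug, from the questioning, or from both, and a pooled table cannot tell these apart.

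New events in the first days after stopping are the most exposed. Cognitively impaired participants may first be asked about them, in general terms, about two weeks later. Onset dates would then be uncertain even when the event is recalled. The causality guidance in Appendix 3 asks "Was the Sponsor's product discontinued or dose/exposure/frequency reduced" and whether the event then improved, so dating around the last dose has a use beyond the table.

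The groups are small. With 21 participants on MK-8189 and 7 on placebo, one participant whose event is missed changes that event's incidence by 1/21 = 4.8 or 1/7 = 14.3 percentage points.

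**Working it through.** The plan has no power, precision or capture calculation to reproduce. The check is a count of scheduled contacts, followed by an illustration on a stated assumption.

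**1. Contact density.**
- On drug, Titrations 1 and 2: visits on Days 1, 4, 7, 14, 21 and 28 make 6 visits and 28 − 6 = 22 calls. Titration 3 adds Day 10: 7 visits and 21 calls. Either way, 28 contact days in 28 = 1.0 per day.
- Off drug: 1 contact in 14 days = 0.071 per day, a 14-fold drop.
- Off drug with two contacts (an early poststudy visit plus the call, or Visit 9 held on Day 29): 2/14 = 0.143 per day, a 7-fold drop.

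**2. Off-drug share of the AE window.** With last dose on Day s and a window of s + 14 days, the share is 14/(s + 14).

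| Last dose | Window (days) | Off-drug share |
|---|---|---|
| Day 28 | 42 | 33% |
| Day 21 | 35 | 40% |
| Day 14 | 28 | 50% |
| Day 7 | 21 | 67% |

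**3. Delay before the question.** Section 2.2.2 gives a half-life of about 10.9 h. Five half-lives are 54.5 h = 2.3 days. An event arising then would be asked about 14 − 2.3 = 11.7 to 16 − 2.3 = 13.7 days later, if no other contact intervenes.

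**4. What the loss could be (assumption, not data).** Suppose that onset is uniform over the window and that the chance of an event being reported decays exponentially with time constant τ. Mean capture for a gap of L days is (τ/L)(1 − exp(−L/τ)). For τ = 7 this gives 0.432 at L = 14 and 0.932 at L = 1, a ratio of 0.46. The share of a participant's events missed, relative to daily questioning throughout, is the off-drug share × (1 − ratio).

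| τ assumed (days) | Off-drug capture relative to daily | Missed, completer | Missed, Day 7 stop with a 14-day gap | Off-drug capture with one mid-interval contact |
|---|---|---|---|---|
| 7 | 0.46 | 0.179 | 0.357 | 0.68 |
| 14 | 0.66 | 0.115 | 0.230 | 0.82 |
| 30 | 0.81 | 0.063 | 0.125 | 0.91 |
| 60 | 0.90 | 0.034 | 0.067 | 0.95 |

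Nothing in the documents fixes τ. The range shows only that the loss could be trivial or material.

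**5. Early stoppers.** Take a last dose on Day 7, so that the off-drug window is Days 8 to 21.
- If Section 7.1 is followed and SoA visits continue, Days 14 and 21 fall inside the window: at least two contacts, against one for a completer.
- If Section 8.1.9 is followed, there can be poststudy procedures around discontinuation and a call at the end of follow-up: again two contacts, although the gap between them can still be about 14 days.

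Neither path gives fewer contacts per day than a completer has. What rises is the off-drug share in step 2.

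**The case against.** **The end of the calls is not explicit.** Section 4.2 mentions daily calls in a sentence about safety throughout the study, and footnote c ties them to outpatient status. This stands as an ambiguity. The Intervention Period heading and the calls' dosing-compliance purpose make dosing-only the better reading, and the SoA has no visit between Visits 9 and 10. The end should be stated.

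**Caregivers can report.** Section 8.4 allows it, and inclusion criterion 4 requires face-to-face contact on at least four days a week. This reduces the risk. It does not remove it, because no scheduled contact prompts the caregiver before the poststudy visit.

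**Early stoppers are the worst recorded.** A reader might infer this from the rising off-drug share. The documents do not support it: contact density is no lower on either path in step 5. The real fault is that Sections 7.1, 8.1.9 and 8.10.5 do not agree on what these participants receive.

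**The arm with more early stops has its AE count biased down.** This too might be inferred. Both blinded arms share one schedule and no between-arm test is planned. Bias between arms needs stopping or off-drug events to differ by arm, and events then to be missed. Neither is shown. An AE that causes discontinuation begins on drug under daily contact, so the second primary endpoint is little affected.

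**Dechallenge cannot be dated.** This goes too far. Sections 8.1.9 and 8.4.3 and Appendix 3 require events already present to be followed. The exposure is mainly in events that start after the last dose. For the others, some resolution dates may be less precise.

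**Conclusion.** The point holds in a limited form. Scheduled AE contact falls 14-fold after the last dose (7-fold where a second contact occurs), over 33% of a completer's AE window and a larger share for those who stop early. Both periods enter one primary summary without a split. On-drug and off-drug AE rates within an arm are therefore not comparable, and new events soon after stopping are at risk of being missed or poorly dated.

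This rests on reading the daily calls as ending with dosing and on a window of dosing days plus 14. Under-recording itself is a credible inference from MMSE-2 scores of 10 to 24, open-ended questioning and a gap of up to about 16 days. Its size is not documented, and the figures in step 4 depend wholly on the assumed τ. This is a worthwhile, inexpensive improvement to a small descriptive study. It does not invalidate the design.

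**What to change.** 1. In the SoA (Section 1.3, call row and footnote c), state when the daily calls end.
2. In the SoA and Section 8.10.6, add about three AE calls in the 14 days after the last dose, weighted to the first week, for completers and early stoppers alike. State in Section 8.10.5 that these calls lie outside the discretionary subset.
3. Reconcile Sections 7.1, 8.1.9 and 8.10.5 on the follow-up that early stoppers receive.
4. In Section 9.6, tabulate on-drug and off-drug AEs separately, each with days observed. This is needed even with the added calls: three calls plus the visit give 4/14 = 0.29 contacts per day, still 3.5 times sparser than daily.

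**Cost.** 3 calls × 28 participants = 84 calls, against 22 × 28 = 616 planned under Titration 1 or 2. That is 84/616 = 14% more, made by staff who already call daily. There is also one extra table split. No clinic visit is added and dosing does not change.
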